9.3 Definition of Populations

The study will occur within the eight VISN-1 VA medical centers (VAMC) located across six New England States. The medical centers are: Bedford VAMC; Boston Healthcare System; Central Western Massachusetts; Connecticut Healthcare System; Maine Healthcare System, Manchester VAMC, Providence VAMC, and White River Junction.

Inclusion and exclusion criteria:

Inclusion criteria: 1) post-9/11 Veteran applying for MSD-related compensation (specified as back, neck, shoulder, or knee pain), as ascertained from filed claim, 2) reports a score of ≥ 4 (threshold for moderately severe pain) on the BPI's Pain Severity subscale (average of four pain intensity items); 3) availability of a landline or cellular telephone for SBIRT-PM.

Exclusion criteria: 1) reports inability to participate during the study enrollment call; 2) received three or more non-pharmacological pain treatment modalities within the last 12 weeks from VA, and 3) participation in another PMC3 study as evidenced by a research protocol alert for that study at the time the study invitation letter is mailed.

Participants who complete the baseline assessment and are randomized to their treatment assignment will be the Intent to treat (ITT) population for analysis. The per-protocol analyses will specify patients who participated the treatment and be conducted by including a variable indicating participation (Yes/No) in the ITT analyses. We will give precedence to the results of the ITT analysis over the PP analysis.

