Counselors will determine on a case-by-case basis when to conduct this additional session based on when services become more available at each site and veteran preferences. Only one session will be permissible during this week 12-32 period, regardless of the number of sessions completed during Weeks 1-12. All participants in the SBIRT-PM condition currently are within 32 weeks post-randomization and thus eligible to receive the additional session. The additional counseling session will remain part of the protocol for the duration of the trial.

Usual Care.

A Veteran who completes a Compensation examination ordinarily has no further treatment, referral or debriefing as part of the Compensation examination. Veterans assigned to the control condition will be contacted by the Project Director and will be told they were assigned to the condition without additional study counseling. Veterans will be reminded that they should continue to pursue whatever counseling they need outside the study.

Justification for No Additional Referral Control Condition. No additional treatment is "treatment-as-usual" when a Veteran applies for service-connection. However, no treatment that a Veteran would otherwise get without participating in this study will be withheld. An active control group is important when an extensive intervention is being tested and it is important to determine if the intervention's efficacy apart from non-specific benefits from the time and effort expended by the clinician. However, the need for an active control group is less compelling when compared to a relatively brief intervention⁹⁸ and when conducting a pragmatic trial where the emphasis is testing the effectiveness of innovations that improve upon usual clinical care.⁹⁹

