For the data analyses, adherence to SBIRT-PM counseling will be dichotomized (“Having received counseling” Yes/No). This approach is being taken because SBIRT-PM’s duration and intensity is not hypothesized to relate to outcome; a Veteran might, in a single session, take steps to engage in non-pharmacological pain treatment that require minimal follow-up. Conversely, a Veteran with more follow-up sessions might have more because the Veteran is more ambivalent about non-pharmacological pain treatments and is receiving more counseling because of more need for it. After the completion of the intent-to-treat analyses, the adherence indicator will be added to examine it as a potential mediator of response in the primary outcome analyses.

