9.6 Data Analyses

All variables (Intervention, covariates and outcomes) will be described with the use of the approximate summary statistics (mean, median, interquartile range, and percent). Multivariate models will be used following the examination of bivariate tests of outcomes by intervention group. A successful outcome will be either a reduction in pain severity or number of substance use above the “no intervention” threshold in the ASSIST or toxicological analysis of nail clippings. The model type will be selected based on meeting of modeling assumptions including the outcome distribution; Potential models will include linear and non-linear mixed-effects (Poisson (with over-dispersion), negative binomial, binary outcome) regression modeling. If there is a large skew with many zeros (which is quite possible where the outcome is change in the number of substances no longer needing intervention), we will use a negative binomial. If the distribution is a combination of 0's (no change) and 1's (change to level of “no need for intervention” in one substance) with very few outcomes greater than 1, a binomial distribution will likely be used. A Poisson model will be used if there are very few successes and they have a Poisson distribution.

These common rules will be used for guidance:

- Poisson distribution, if mean = variance
- Binomial distribution, if mean > variance
- Negative binomial distribution, if mean < variance

The covariance structures will be explored to determine which (unstructured, compound symmetry, autoregressive) is the most appropriate in mixed models. Selection will be based on the lowest AIC. An intervention by time interaction will be tested in the models – this will show the effect of the intervention on the outcome compared to controls.

Change in Pain: We anticipate using linear mixed-effects modeling to test the effect of SBIRT-PM on the 12-week value of the BPI, if it is a normally distributed outcome. We will in addition test simultaneously the unique effects of treatment on pain outcomes at week 12 and week 36, controlling for baseline differences, and test the equality of these parameters using the Wald test.

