Change in Substance Use: We anticipate using non-linear mixed-effects (Poisson, negative binomial, binary outcome as discussed above) regression modeling to test the effect of SBIRT-PM on the number of substances requiring intervention (according to the ASSIST), a count outcome. One subset of analyses will use risk sets

(at least 1 substance at baseline, at least 2 substances at baseline, etc.) to analyze substance risk changes in substance users. We will also test the equality of treatment effects at weeks 12 and 36 as described above.

We have identified stratification variables to account for error variance as a recommended good practice. Key covariates to be included in the model are depression, TBI, and mental health diagnoses (grouped into multiple more homogenous groupings, such as mood and psychotic disorders) as these are highly related to pain perception and substance abuse as well as the urn covariates—namely sex, race, ethnicity, self-reported illicit drug use and site. The strata used for the urn randomization are only to better ensure balance on key characteristics. Their main effects will not be interpreted in the analysis, though they will be examined as potential modifiers of the intervention effect. We will also consider as potential covariates: distance to nearest VA medical center, number of pain treatment modalities used at baseline, reasons patient might drop out of the study, and the probability of withdrawal. Opioid-use will be examined as a mediator as well as a tertiary outcome. Actual participation in SBIRT-PM (Y/N) will be examined as a mediator of response.

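### The per-protocol analysis adds a self-selected participation indicator to the ITT model; read alone, its coefficient is the effect of receiving SBIRT-PM only if attenders and non-attenders share the same prognosis given the covariates

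*Combined protocol and SAP*

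**What the plan says.** Section 9.3 takes everyone randomized after baseline as the ITT population. It states that the per-protocol analyses will "be conducted by including a variable indicating participation (Yes/No) in the ITT analyses", and adds: "We will give precedence to the results of the ITT analysis over the PP analysis".

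The same variable has a second role. Section 5.4 reduces adherence to whether any counseling was received, Yes or No, and says that after the ITT analyses "the adherence indicator will be added to examine it as a potential mediator of response in the primary outcome analyses". Section 9.6 repeats this: "Actual participation in SBIRT-PM (Y/N) will be examined as a mediator of response".

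On who can be a Yes: in Section 5.1 (Usual Care), control Veterans are told "they were assigned to the condition without additional study counseling". In Section 6.2.5, a Veteran may decline counseling and stay in the assessments.

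On adjustment, Section 9.6 says "Key covariates to be included in the model are depression, TBI, and mental health diagnoses", together with the urn factors including site, and for pain it specifies "controlling for baseline differences, and test the equality of these parameters using the Wald test". Distance to a VA facility, baseline modalities and probability of withdrawal are only to be considered.

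On timing, Section 9.3 gives no date by which participation must have occurred. Section 5.1 allows an extra call: "Only one session will be permissible during this week 12-32 period, regardless of the number of sessions completed during Weeks 1-12".

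**The concern.** Participation is decided after randomization, partly by the Veteran. Because it is No throughout usual care, a model holding both arm and participation estimates the participation term from attenders and non-attenders within SBIRT-PM. If attenders would have fared better or worse anyway, that difference enters the coefficient. The planned covariates can shrink it but do not guarantee its removal. Baseline motivation to engage in pain treatment is collected (Sections 6.1 and 6.2.2) but is not among the covariates named in Section 9.6.

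The plan does not say which coefficient is the per-protocol result, what it estimates, or under what assumption. The labels per-protocol and mediator both invite a causal reading. Taken that way, the result could show a benefit of counseling that does not exist or hide one that does, on both primary outcomes.

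A smaller gap concerns timing. Outcomes are measured at weeks 12 and 36. With no cut-off, a first session held after the week-12 assessment could mark a Veteran as a participant for an outcome already recorded.

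**Working it through.** **Inputs from the documents.** Attendance p = 0.80 (pilot, Section 10.3.5). From Section 9.2: 400 evaluable per arm, d = 0.25, power .90 and alpha .025. Section 9.2 sets that alpha for the sample-size calculations; no alpha is given for the per-protocol analysis, so it is borrowed here.

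**Assumed.** g, in SD units with benefit positive, and a baseline to follow-up correlation rho of 0.4 to 0.6.

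**The plan's own figure.** n per arm = 2(2.241 + 1.282)²/0.25² = 397.2, so 398; the plan's 400 agrees. Power at 400 is .902. 400/0.73 = 548, and twice that is 1096, as stated.

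**What the coefficients estimate.** Let tau be the effect of receipt among attenders, and g the difference between attenders and non-attenders in outcome without counseling, after all model covariates. Suppose assignment alone does nothing for non-attenders. In a linear model with arm and participation:

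- participation coefficient = tau + g
- arm coefficient = -p × g
- arm + p × participation = p × tau = ITT
- participation + arm/p = tau

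With ITT = 0.25, tau = 0.25/0.80 = 0.3125. The coefficients are then:

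| g | participation | arm | participation + arm/p |
|---|---|---|---|
| -0.3 | 0.0125 | 0.24 | 0.3125 |
| -0.2 | 0.1125 | 0.16 | 0.3125 |
| 0 | 0.3125 | 0 | 0.3125 |
| 0.2 | 0.5125 | -0.16 | 0.3125 |
| 0.3 | 0.6125 | -0.24 | 0.3125 |

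Simulation agreed within sampling error.

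**Standard errors, unadjusted, SD 1.**

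- Participation: sqrt(1/320 + 1/80) = .125
- ITT: sqrt(2/400) = .0707
- Complier: .0707/0.80 = .0884

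**False significance, no true effect, no covariates.** The rate is P(|Z + g/.125| > 2.241). For g = 0.1, 0.2 and 0.3 this gives 7.6%, 26.1% and 56.3%. Simulation with 4,000 trials per setting gave 8.1%, 24.6% and 55.8%, while the ITT test stayed near 2.5%.

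**If the gap is a raw baseline gap of 0.3 SD.** This is a different quantity from g. Adjusting for baseline leaves g = 0.3(1 - rho), and the standard error becomes .125 × sqrt(1 - rho²):

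| rho | remaining bias | SE | falsely significant |
|---|---|---|---|
| 0.4 | 0.18 | .115 | 25% |
| 0.5 | 0.15 | .108 | 20% |
| 0.6 | 0.12 | .100 | 15% |

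**The opposite sign.** With a raw baseline gap of -0.3 and tau = 0.3125, the participation coefficient averages 0.13 to 0.19 and is significant in 14% to 38% of trials. The complier estimate averages 0.31 and is significant in about 95% to 98%.

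**Precision at g = 0, tau = 0.3125.** Unadjusted power is 60% for participation and 90% for the complier estimate. Baseline-adjusted, participation reaches 69% to 81% and the complier estimate about 95% to 98%.

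**ASSIST on a logistic scale.** In one constructed case, usual-care conversion is 11% in would-be attenders and 6% in others, which is 10% overall, and receipt adds .2125, giving 27% in the SBIRT-PM arm. Participation + arm/p is then 1.316, against a true complier log-odds ratio of 1.348. The linear identity is inexact there, by about 2%.

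**The case against.** The strongest reply is that any harm is conditional and contained. ITT has precedence, and nowhere does the plan say it will report the participation coefficient as the effect of receipt. The planned linear model also holds what is needed: participation + arm/p gives the complier effect, and Section 10.3.5 commits to reporting the share of participants at each number of sessions. This stands as a limit on severity. It does not close the gap, because no section names that combination, its standard error or its assumption.

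Second, g is assumed, and the unadjusted rates ignore covariates to which the plan commits. That is fair. At a raw baseline gap of 0.1 SD with baseline adjustment, the false-significance rate is only 4% to 5%, and the other covariates could lower it further. The rural phone coverage and local reputation mentioned in Section 10.3.5 are given as site-level obstacles, not as evidence about prognosis, and site is a covariate.

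Third, a complier estimate swaps one untestable assumption for another. True, but randomized assignment, no counseling in usual care and high pilot attendance suit it, and it needs no value for g.

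A reader might go further than the documents allow in four ways:

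- That the primary conclusion is biased. It is not: the ITT inference, its alpha and the sample size are unaffected.
- That attenders are known to have the better prognosis. Section 5.4 says more sessions may reflect greater ambivalence or need, but that concerns the number of sessions, not any against none.
- That the nonlinear ASSIST models go badly wrong. The one check shows inexactness of about 2%, not a material error.
- That receipt differs by a known amount between weeks 12 and 36. No figure supports any split.

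**Conclusion.** The point holds as a specification gap in supplementary analyses. Read alone, the participation coefficient equals the effect of receipt only if g = 0 given the covariates, and calling the variable a mediator does not change that. The algebra is exact for a linear pain model with no counseling in usual care and no effect of assignment on non-attenders. The same selection problem reaches the ASSIST models without the exact decomposition.

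The size depends on g, which the documents do not give, so the error rates above illustrate and do not predict. The loss of precision does not depend on g: at 80% attendance the complier standard error is .0884/.125 = 0.71 of the participation coefficient's. The change is worth making because it is cheap, but the primary inference does not turn on it.

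**What to change.** In Section 9.3, replace the participation-coefficient analysis with a supplementary complier-average effect of receiving at least one SBIRT-PM session, with randomized arm as the instrument and the ITT covariates.

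- **BPI severity:** two-stage least squares. Without covariates this equals ITT/p.
- **ASSIST:** the same estimator on a difference scale (mean count, or proportion if the binary form is used), with robust standard errors.
- **Receipt:** count only a first session held before the assessment being analysed, separately for weeks 12 and 36. Two outcomes at two times make four fits.
- **Assumption:** state that assignment alone is taken to have no effect on outcome, and give a sensitivity range labelled as assumed. For example, at a fixed ITT of 0.25, a direct effect of 0.05 or 0.10 SD in everyone assigned leaves (0.25 - 0.05)/0.80 = 0.25 or (0.25 - 0.10)/0.80 = 0.19 for receipt, against 0.31 with none.

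In Sections 5.4 and 9.6, if the participation coefficient is still reported, label it associational and not per-protocol or mediation. Report it with the arm coefficient and p, and add the baseline motivation score as a covariate.

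Cost: SAP wording and four linear instrumental-variable fits on outcomes and session logs already collected. ITT, alpha and sample size do not change. The downsides are an interval about 25% wider than ITT's at p = 0.80 (1/0.80 = 1.25), an exclusion restriction that cannot be tested, an ASSIST estimate on a different scale from its ITT model, and supplementary fits outside the planned mixed-model framework.

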9.4 Interim Analyses and Stopping Rules

No interim analysis is planned. An in-person version of the proposed intervention was tested in a completed study by this team ([name] et al., 2018). There were no study-related adverse events.

There are no stopping rules.

9.5 Outcomes

9.5.1 Primary Outcome

The two primary outcomes are pain severity as measured by the BPI and the number of substances above the “no intervention” threshold in the ASSIST. We initially planned that when a positive toxicology result disagrees with a self-report of no use, the middle value on the ordinal scale (the indication to receive brief intervention) would be derived and used as the primary substance use outcome. However, only 64% of participants returned nail samples at baseline, and this percentage dropped to 58% and 49% at week 12 and 36, respectively, among participants with completed ASSIST assessments. Further, depending upon the substance and timepoint, between 43% and 48% of participants self-reporting a level of substance use that does not require an intervention, the group whose substance use classification would change with positive nail toxicology, did not have toxicology results. Given the amount of missing toxicology data and that nails do not measure intervention need directly like the ASSIST, we plan to base our primary substance use outcome on the ASSIST measure only. This change does not compromise our estimated power since the number of participants self-reporting a level of risky substance use that requires an intervention on the ASSIST (N=571) exceeds our assumed total sample size for this outcome (N=352) used in power analyses. The BPI and ASSIST are collected at baseline, week 12 and week 36.

9.5.2 Secondary Outcomes

Secondary outcomes related to pain include non-pharmacological pain management service utilization, pain interference with life activities (BPI), overall pain (PEG), and overall health. The non-pharmacological pain management service utilization will be

summed across 13 possible modalities (injection; physical therapy; chiropractic care; acupuncture; TENS; Spinal cord stimulator; cognitive behavioral therapy; mindfulness/acceptance and community therapy; treatment involving teaching about coping with pain; yoga, Tai chi or Reiki; massage treatment; other treatment not already mentioned) as well as examined by individual modalities where sufficient sample size is present.

Secondary outcomes related to substance use will include severity measures for individual substances generated by the ASSIST, as well as toxicology results for individual substances.

9.6 Data Analyses

All variables (Intervention, covariates and outcomes) will be described with the use of the approximate summary statistics (mean, median, interquartile range, and percent). Multivariate models will be used following the examination of bivariate tests of outcomes by intervention group. A successful outcome will be either a reduction in pain severity or number of substance use above the “no intervention” threshold in the ASSIST or toxicological analysis of nail clippings. The model type will be selected based on meeting of modeling assumptions including the outcome distribution; Potential models will include linear and non-linear mixed-effects (Poisson (with over-dispersion), negative binomial, binary outcome) regression modeling. If there is a large skew with many zeros (which is quite possible where the outcome is change in the number of substances no longer needing intervention), we will use a negative binomial. If the distribution is a combination of 0's (no change) and 1's (change to level of “no need for intervention” in one substance) with very few outcomes greater than 1, a binomial distribution will likely be used. A Poisson model will be used if there are very few successes and they have a Poisson distribution.

These common rules will be used for guidance:

- Poisson distribution, if mean = variance
- Binomial distribution, if mean > variance
- Negative binomial distribution, if mean < variance

The covariance structures will be explored to determine which (unstructured, compound symmetry, autoregressive) is the most appropriate in mixed models. Selection will be based on the lowest AIC. An intervention by time interaction will be tested in the models – this will show the effect of the intervention on the outcome compared to controls.

Change in Pain: We anticipate using linear mixed-effects modeling to test the effect of SBIRT-PM on the 12-week value of the BPI, if it is a normally distributed outcome. We will in addition test simultaneously the unique effects of treatment on pain outcomes at week 12 and week 36, controlling for baseline differences, and test the equality of these parameters using the Wald test.

Change in Substance Use: We anticipate using non-linear mixed-effects (Poisson, negative binomial, binary outcome as discussed above) regression modeling to test the effect of SBIRT-PM on the number of substances requiring intervention (according to the ASSIST), a count outcome. One subset of analyses will use risk sets

(at least 1 substance at baseline, at least 2 substances at baseline, etc.) to analyze substance risk changes in substance users. We will also test the equality of treatment effects at weeks 12 and 36 as described above.

We have identified stratification variables to account for error variance as a recommended good practice. Key covariates to be included in the model are depression, TBI, and mental health diagnoses (grouped into multiple more homogenous groupings, such as mood and psychotic disorders) as these are highly related to pain perception and substance abuse as well as the urn covariates—namely sex, race, ethnicity, self-reported illicit drug use and site. The strata used for the urn randomization are only to better ensure balance on key characteristics. Their main effects will not be interpreted in the analysis, though they will be examined as potential modifiers of the intervention effect. We will also consider as potential covariates: distance to nearest VA medical center, number of pain treatment modalities used at baseline, reasons patient might drop out of the study, and the probability of withdrawal. Opioid-use will be examined as a mediator as well as a tertiary outcome. Actual participation in SBIRT-PM (Y/N) will be examined as a mediator of response.

Per NIH policy, because there is considerable data suggesting the importance of race, ethnicity and sex on the study outcomes (pain, substance use and service use), we will conduct an analysis that examines sex and race/ethnicity as moderators of treatment response. These analyses will be conducted through the inclusion of interaction effects in models so sex and race/ethnicity effects can be formally tested. In light of the differences in substance use, body habitus, and substance metabolism between men and women, we will include a sex interaction term for the analysis of the relationship between self-reported levels of substance use and levels of ETG found in nail clippings. While the use of subgroup analysis might be interesting to look at sex-specific characteristics such as the influence of pregnancy or stage of menstrual cycle, we currently have no relevant covariates making the case for this type of sub-analysis.

Sensitivity Analysis

We anticipate some missingness will occur not completely at random. In general, more sensitive information such as use of illicit substances is less likely to be shared by participants when responding to an interviewer. Based on our previous study (R34), we anticipate there might be a difference in the follow-up rate between Veterans in the two arms of the trial, with veterans in the usual care arm more frequently dropping out. We have created scenarios to minimize missing data through design considerations (i.e., increasing our payment scale as incentive, regular reminder calls), but our analytic plan includes the investigation of missingness. Patterns of missingness will be examined by each individual covariate in the data (univariate, monotone or non-monotone). Chi-squares and t-tests will be run to see if missingness is related to other variables in the analysis (for example: intervention status, substance use). We intend to utilize multiple imputation in the case of variables missing either completely at random or at random. To reduce the likelihood of MNAR, the multiple imputation model will include “auxiliary variables” which are highly correlated with both the variable that has missing data and the probability that the variable is missing. Sensitivity analyses will be conducted as part of the multiple imputation procedure in SAS 9.4 (PROC MI).

Sources of data

Data for the study are drawn from patient self-report, VA electronic medical records of VA and community care, and the C&P examination. Veterans requesting a Compensation & Pension evaluation for knee, shoulder, neck or back pain may or not be receiving services from the VA. Persons who get all their care outside of the VA will not have readily accessible medical records, while those persons who get some care in the VA but are sent out to community care for distinct services (such as non-pharmacological pain management) will have medical records of both types of care. In addition, those veterans who had not used any VA services prior to their C&P request may then enter VA care following their C&P exam and will have EMR available only in the follow-up period. The lack of EMR data of non-users of the VA will affect both the intervention or control arms of the study, and there is no reason to believe its effect will be differential.

Acknowledging the variability in availability of EMR information, all subjects will have self-reported and C&P data regarding service use as well as diagnoses. We will examine the concordance of self-reported and EMR-obtained information to estimate the impact of having no EMR data in the non-users of the VA. We will conduct a sensitivity analysis sub-setting the analyses only to those persons with available EMR (as well as self-reported and C&P data).

Cost-Effectiveness Analysis

The relative cost-effectiveness of SBIRT-PM will be assessed using both incremental cost-effectiveness ratios (ICERs) and cost-effectiveness acceptability curves (CEACs). ICERs and CEACs will be calculated from the provider (i.e., VISN and medical center) perspective. Using the cost estimates described in the Assessment subsection, we will calculate ICERs for minimal clinically important differences (MCID) between baseline and week-36 assessments in three primary outcomes: self-reported pain, risky alcohol use, and morphine-equivalent doses of opioid analgesic medication use.

- Pain. Self-reported pain severity and interference will be measured by the Brief Pain Inventory (BPI). A MCID in pain severity will be a 30% reduction in ratings on this BPI subscale from baseline to week 36. The MCID for pain functioning will be a 1-point change in the BPI pain interference subscale. We have followed the guidelines Erin Krebs followed in the SPACE trial for selecting an MCID. She states in her group's 2018 JAMA report of the SPACE trial: "Following consensus guidelines, this trial used a 1-point difference as the MCID for BPI interference and BPI severity, and used a 30% reduction from baseline as MCID for moderate improvement."
- Substance Use. As noted earlier, the ASSIST categories represent what clinicians consider a clinically important difference, in that a difference the differences in risk category guide treatment. Therefore, we will consider a net decrease of one risk category (i.e. need for less overall treatment) across substances as the MCID.

The ICERs will measure the incremental cost of using SBIRT-PM to produce a MCID in each of the outcomes. We will conclude SBIRT-PM's cost-effectiveness for each outcome based on its ICER with respect to the threshold value placed by decision makers on the effect for that outcome. By using multiple outcomes, we can determine

the robustness of our cost-effectiveness findings and provide a more fine-grained cost-effectiveness analysis to address different priorities that stakeholders may have.^{186, 187}

To illustrate the uncertainty associated with ICER point estimates, cost and effect estimates of SBIRT-PM will be bootstrapped (with 2,000 replicates) to produce confidence intervals around the ICERs and to produce CEACs for each outcome measure.¹⁸⁸ CEACs quantify the uncertainty in the cost-effectiveness analysis by showing the probability that the intervention is cost-effective with respect to any given threshold value.¹⁸⁸⁻¹⁹⁰ Intuitively, as the threshold value of a MCID in a given outcome increases, the strategy that produces that effect most efficiently becomes increasingly more likely to be the most cost effective, even though incremental costs are incurred. Similarly, as the threshold value of a MCID in a given outcome decreases, the strategy that has the lowest cost becomes increasingly more likely to be the most cost-effective. Finally, sensitivity analyses will be conducted to determine the robustness of the cost-effectiveness results to alternative assumptions about a wide variety of implementation parameters (e.g., cost of inputs).

Budget Impact Analysis.

To demonstrate the financial feasibility of adopting SBIRT-PM, a budget impact analysis will be conducted. The per-person cost of SBIRT-PM will comprise the cost of delivering the intervention plus the cost of the VA-funded services used by the participant in the SBIRT-PM condition over and above the cost of those used by individuals in UC, minus the yearly patient allocation (VERA dollars) assigned to that participant. The total projected yearly cost to a given medical center of SBIRT-PM will be the per-person cost times the total number of Veterans applying for compensation and pension for a musculoskeletal condition times the expected rate of uptake.

Analyses of NLP Algorithms

We will identify the use of non-pharmacological pain modalities through self-report from the participants as well as two different approaches to the extraction of healthcare utilization data from electronic medical records. Medical record extraction of 1.) Structured data - stop codes indicating use of these modalities, and 2.) Unstructured data - domains identified in the application of the NLP method to the medical record data of study participants. Two independent researchers will identify words/snippets that suggest use of specific non-pharma modalities and rate enough snippets to have software reliably generate an algorithm to rate all patients included in the study on each modality (machine learning). As we expect false positive reports of use of a modality to be unlikely, identification of use during an assessment period by any of the three methods (self-report, medical record stop codes and NLP) will be considered use. The agreement between these different measures will be described by cross-tabs.

